7.4. Study Monitoring

7.4.1. Adverse Events

The UNC Safety Monitoring Committee (SMC) will review and assess select expedited adverse events (EAE) reports for potential impact on the study participant safety and protocol conduct as per, guidance documents, and standard operating procedures (SOPs) as applicable. Summary reports of AEs will be shared weekly with the medical monitor(s). SAEs will be reported through the Covance SAE reporting protocol within 24 hours to the medical monitor(s). The EIDD-2801 principal investigator, co-investigators, and Ridgeback medical officer will review all deaths on a weekly basis in a blinded fashion.

7.4.2. Interim Review

The protocol team will monitor the conduct of the study via regular summaries of screening, accrual, study and study treatment discontinuation, and data and specimen completeness. The UNC SMC will monitor safety regularly.

Detailed plans for study monitoring are outlined in a Study Progress, Data, and Safety Monitoring Plan (SPSMP) developed prior to enrollment of the first participant.

8. CLINICAL MANAGEMENT ISSUES

8.1. Toxicity

Criteria for participant management, dose interruptions, dose adjustments and discontinuation, or changes in treatment will be described only for toxicities attributable to the study drug. The grading system for drug toxicities is located in the DAIDS AE Grading Table (see Section 7.3.2).

NOTE: The study team must be notified via e-mail within 72 hours regarding toxicities that result in a change in study regimen.

It is possible that some participants will experience transient or prolonged AEs during the study. For any concerning AEs that are felt to require clinical intervention, participants should be instructed to contact their health care provider or seek urgent or emergent care, or 911 should be called, as appropriate.

8.2. Management of Side Effects of EIDD-2801

Only toxicities related to study medications provided through this study will be considered in the toxicity management section. The grading system is located in the Division of AIDS Table for Grading the Severity of Adult and Pediatric Adverse Events (DAIDS AE Grading Table), Version 2.1, March 2017: http://rsc.tech-res.com/clinical-research-sites/safety-reporting/daids-grading-tables.

8.3. Grade 1 or 2

Participants who develop a Grade 1 or 2 AE or toxicity may continue study medications without alteration of the dosage, except as stated in sections below. For participants experiencing Grade 1 or 2 AEs who choose to discontinue all study medications, the site investigator should complete premature discontinuation of study therapy evaluations, contact the study leadership team, and the participant should be encouraged to complete follow-up protocol study evaluations.

NOTE: If participants discontinue study medications due to experiencing Grade 1 or 2 AEs, this should be noted in the eCRF as the reason for discontinuation.

8.4. Grade 3

If the investigator (in consultation with the medical monitor at the investigator's discretion) has evidence that the AE has NOT been caused by study medications, dosing may continue. Participants who develop a Grade 3 AE or toxicity thought to be related to a study medication, except as stated in section below, should have their study medication discontinued. The participant should be reevaluated daily until the AE resolves or returns to baseline. The study leadership team must be notified and the relevant eCRF completed. Participants experiencing Grade 3 AEs requiring permanent discontinuation of all study medications should be followed daily until resolution of the AE and encouraged to complete the premature discontinuation of study therapy and follow-up protocol study evaluations.

8.5. Grade 4

Participants who develop a Grade 4 symptomatic AE or toxicity related to study product, will have the study medication permanently discontinued, except as stated below. Participants experiencing Grade 4 AEs requiring permanent discontinuation of all study medications should be followed daily until resolution of the AE and encouraged to complete the premature discontinuation of study therapy and follow-up protocol study evaluations.

Situations where study product does not need to be discontinued:

- Participants with Grade 3 or 4 asymptomatic creatine kinase (CK) elevation may continue study medication if the investigator has evidence that the CK elevation is not suspected to be related to the study medications.
- Participants with new Grade 3 or 4 AEs that are considered to be COVID-19 related and not study product related may continue study product following discussion with one of the study team leads.

8.6. **Pregnancy**

The study products may not be given in pregnancy.

8.7. Breastfeeding

The study products may not be given to women who are breastfeeding.

9. CRITERIA FOR DISCONTINUATION

The investigator, in consultation with the Sponsor, may decide to discontinue a subject from dosing or from the study based on their clinical judgement and/or in consultation with the Safety Monitoring Committee.

9.1. Permanent and Premature Treatment Discontinuation

Participants may have study treatment discontinued for reasons including, but not limited to, the following:

- Drug-related toxicity (see Section 8 CLINICAL MANAGEMENT ISSUES).
- Participant experiencing an SAE that is considered at least possibly related to study drug.
- Request by participant to terminate treatment.
- If platelet count drops below 75,000/mm³ treatment will be discontinued
- NOTE: The reason for treatment discontinuation should be documented (e.g., concern for AE, lack of efficacy, or other reason).
- Clinical reasons believed life threatening by the physician, even if not addressed in the toxicity section (Section 8.1) of the protocol.
- Pregnancy.

9.2. Premature Study Discontinuation

Participants may be discontinued from the study for reasons including, but not limited to, the following:

- Request by the participant to withdraw consent.
- Request of the health care provider if she or he thinks the study is no longer in the best interest of the participant.
- At the discretion of the IRB/EC, FDA, Office for Human Research Protections (OHRP), other government agencies as part of their duties, investigator, or sponsor.

In the event that a participant prematurely discontinues from the study, unless they have withdrawn consent, sites will attempt to obtain information regarding vital status (including date last seen alive, hospitalization, date of death, and primary cause of death) from other sources (such as family members, other designated contacts, or clinic records).

10. STATISTICAL CONSIDERATIONS

10.1. General Design Issues

This is a phase IIa, double-blind, placebo-controlled trial to evaluate the safety, tolerability and antiviral activity of EIDD-2801 as measured by viral RNA detection in symptomatic adult outpatients with COVID-19.

10.2. Outcome Measures

Primary and secondary outcome measures listed below will be addressed in the study's primary Statistical Analysis Plan, which will define the content of the Primary Analysis Report. This report will form the basis for the primary study manuscript and results reporting to ClinicalTrials.gov.

10.3. Objectives and Endpoints

Objectives	Endpoints
Prir	nary
To determine if EIDD-2801 reduces the time to viral RNA negativity. Viral RNA negativity will be determined by RT-PCR of NP swabs.	• Qualitative RT-PCR
To determine the safety and tolerability of EIDD-2801 including 1) any adverse events (AEs) leading to early discontinuation of treatment, 2) study drug-related discontinuation of treatment, 3) new grade 3 or higher AE (not already present at baseline), and 4) study drug-related new grade 3 or higher AE.	 All AEs leading to early discontinuation of treatment Study drug-related discontinuation of treatment New grade 3 or higher AE Study drug-related new grade 3 or higher AE

Secon	ndary
Safety Objective: To compare the incidence of grade 2 or higher AEs and drug-related AEs between treatment arms.	Grade 2 or higher AEsDrug-related AEs
Virologic Objectives:	
• To determine if EIDD-2801 reduces the time (days) to negativity of infectious virus isolation in NP swabs from SARS-CoV-2-infected adults. Infectious virus isolation is determined by isolation in Vero cell line cultures.	 Infectious virus detection in NP swab samples cultured on Vero-cell cultures Infectious virus detection by microfoci assay of NP swab samples cultured on Vero-cell cultures
• To determine if EIDD-2801 reduces the shedding of SARS-CoV-2 RNA in NP swabs compared to placebo as measured by median change in RNA at Treatment Days 3, 5, 7, 14, and 28 as determined by quantitative RT-PCR.	• Quantitative RT-PCR
• To determine if EIDD-2801 increases viral RNA mutation rate. RNA mutation rate is measured by Next Generation sequencing.	• Comparison of spike and RNA dependent RNA polymerase gene sequences using Next Generation sequencing
Clinical Objectives:	Patient reported symptoms
• To determine if EIDD-2801 changes the severity and duration of self-reported symptoms of COVID-19	• Time to improvement of new or worsened symptoms (including feverishness, chills, myalgias, headache, sore throat, loss of sense of smell, loss of sense of taste, cough, and difficulty breathing) as measured by a decrease in all of these symptoms from severe/moderate severity to mild/absent or a decrease in mild severity to absent in symptom diary (Absent or returned to pre- COVID-19 level = 0, Mild =1, Moderate =2, Severe =3).
• To determine if EIDD-2801 treatment reduces the proportion of participants who are hospitalized for COVID-19 related illness by Day 28.	• WHO 9-point ordinal scale (see Appendix 1):

Pharmacokinetic Objective:	
• To characterize the PK of EIDD-2801/EIDD- 1931 in patients with COVID-19 following administration of study regimen	• Concentrations of EIDD-2801 and EIDD- 1931 in blood and levels of viral RNA in respiratory and oral samples
• To determine the relationship between drug exposure and viral elimination dynamics including time to clearance.	
Exp	loratory
Exploratory Clinical Objective	
• To determine if EIDD-2801 will prevent the composite endpoint of hospitalization, oxygen desaturation, oxygen requirement, mechanical ventilation, or death by 28 days after study entry. Hospitalization is defined as ≥24 hours of acute care. Oxygen desaturation will be measured using pulse oximetry. Oxygen requirement will be measured using the WHO ordinal scale (see Appendix 1)	• WHO 9-point ordinal scale (see Appendix 1)
Exploratory Diagnostic Objective	
• To determine the comparability between site- collected NP swabs and available OP swabs and available self-collected nasal mid- turbinate swabs for the quantification of SARS-CoV-2 RNA or quantitative culture	• RT-PCR of site collected NP swabs and available OP swabs
• To determine comparability between RNA detection and virus isolation from site-collected NP swabs	• RT-PCR swabs and RT-PCR of NP samples

10.4. Randomization and Stratification

In Part 1 of the study, eligible participants will be randomized using a 1:1 ratio to Arm A or B using permuted blocks. In all subsequent study parts, eligible participants will be randomized using a 3:1 ratio (EIDD-2801:placebo) to Arm C or D (Part 2), Arm E or F (Part 3), Arm G or H (Part 4), Arm I or J (Part 5), Arm K or L (Part 6), Arm M or N (Part 7), Arm O or P (Part 8), or Arm Q or R (Part 9).

In Part 1, randomization will be stratified by "early" versus "late" time from symptom onset, where "early" time from symptom onset is defined by enrollment (i.e., randomization date and time) 0 to ≤ 60 hours from symptom onset and "late" is enrollment (i.e., randomization date and time) >60 to ≤ 168 hours from symptom onset. In subsequent study parts, randomization will not be stratified due to lack of availability of subjects in the "early" time from symptom onset.

10.5. Sample Size and Accrual

The proposed total sample size for the study is up to approximately 172 fully evaluable participants. If participants in a dose group drop out or otherwise have missing or unevaluable primary or key secondary virology endpoint data, additional participants may be enrolled to ensure adequate data at each dose level. The total number of participants to be enrolled will not exceed 204.

For Part 1 of the study, the planned sample size is approximately 44 participants who take the first (confirmed) dose of study treatment (approximately 22 each in Arms A and B).

In subsequent, optional study parts, the sample size **for each part** will include approximately 16 participants who take the first (confirmed) dose of study treatment (approximately 12 participants randomized to an active EIDD-2801 arm and 4 randomized to placebo). Participants who are randomized but do not take the first (confirmed) dose of study treatment will not be followed and will be replaced.

This study is designed to evaluate the antiviral activity of EIDD-2801 by estimating the time (days) until elimination of viral RNA detection in NP swabs in people who receive EIDD-2801 compared to those who receive a blinded placebo. Kaplan-Meier estimation will be used with a corresponding exact, stratified log-rank test (for Part 1) and median time (days) until first non-detectable SARS-Cov-2 NP swabs will be estimated in each trial arm.

Power/Sample Size for Part 1:

The distribution of days until SARS-CoV-2 viral RNA is not detectable (i.e., below the limit of quantification in NP swabs) can be compared between the 2 trial arms (drug vs placebo) using an exact log-rank test. At a 0.10 type I error probability and under the assumptions in Figure 8 and the corresponding table below, there is >85% power to detect a difference (Drug - Placebo) of at least 30% if the evaluable sample size is 19 individuals per arm.

Anticipating up to 10% missing data, enrolling n=44 participants total (approximately 22 per arm) in Part 1 will provide 88% power for the primary endpoint. Power was calculated empirically in R version 3.6.2 using 5000 simulated datasets.

- The power to detect a risk difference (RD) (Drug Placebo) of -30% is 0.88.
- The power to detect a RD (Drug Placebo) of -40% is 0.98.
- The power to detect a RD (Drug Placebo) of -50% is >0.99

The table below contains the assumed data for the viral RNA detection simulations. This assumes collection of NP swabs from all enrolled individuals on Study Days 1, 3, 5, 7, 14, and 28.

[figure not shown]

Figure 8. Probability of SARS-CoV-2 viral RNA detection assumed in power/sample size determination

Study Day	1	2	3	4	5	7	10	14	28
NP swab	Y	Y	Y	Y	Y	Y	Y	Y	Y
Placebo arm	100%	95%	88%	80%	71%	52%	25%	10%	0%
EIDD-2801 Rx arm (RD -20%)	100%	75%	68%	60%	51%	32%	5%	0%	0%
EIDD-2801 Rx arm (RD -30%)	100%	65%	58%	50%	41%	22%	0%	0%	0%
EIDD-2801 Rx arm (RD -40%)	100%	55%	48%	40%	31%	12%	0%	0%	0%
EIDD-2801 Rx arm (RD -50%)	100%	45%	38%	30%	21%	2%	0%	0%	0%

Cumulative probability of viral RNA isolation

Assumes treatment starts 3 to 4 days (i.e., 72 to 96 hours) after symptom onset. NP=nasopharyngeal.

*Extrapolated from Chen, J. JI 2020

Abbreviations: D = Day; NP = nasopharyngeal; Rx = treatment; Y = yes.

Power/Sample Size for Parts 2 to 9:

For Parts 2 to 9, no formal statistical hypotheses will be tested. In consideration of analysis of secondary virology endpoints in these dose range finding cohorts, separate power calculations were done for Parts 2 to 9. For Parts 2 to 9, sample size sensitivity was estimated based on the combined study parts to compare the change from baseline in viral RNA between participants treated with EIDD-2801 versus participants treated with placebo. A total 96 participants in the

active group and 32 participants in the placebo group will achieve 83% power to detect a between group difference of at least 0.6 SD in SARS-CoV-2 viral RNA change from baseline with a significance level of 0.05 using a two-sided test.

Participants who receive placebo will be pooled in the final analyses. The between group comparisons assessment of dose and exposure response will be evaluated based on endpoints of time to undetectable SARS-CoV-2 viral RNA and change in viral RNA over time (including viral RNA baseline-normalized AUC through Day 28), and number (%) of subjects with 1, 2 or $\geq 3 \log_{10} viral RNA$ decline over time.

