10.7.3. Part 1 Analyses

Part 1 will be analyzed separately as an a priori powered study. A Statistical Analysis Plan will be developed that describes the analyses to address the study's primary, secondary, and exploratory objectives.

The following provides an outline of the methods for the main comparisons between randomized arms, particularly for the primary outcome measure.

Analyses involving randomized comparisons will include all randomized participants who received the first (confirmed) dose of study treatment, according to a modified intention-to-treat (m-ITT) approach. Participants who do not receive the first (confirmed) dose will be replaced. Unless stated otherwise, the date of randomization will be the time origin for analysis (Day 1). Additional per-protocol analyses may be performed, particularly for virology efficacy endpoints. Missing data are expected to be uncommon (<5 to 10% of participants). Losses to follow-up will be assumed non-informative and complete-case analyses will be conducted.

This is a virology proof-of-principle study, as such a type I error probability of 10% (α =0.10) will be used throughout, with no planned adjustments for multiplicity or primary or secondary endpoints. Throughout, all statistical tests will be two-sided and "exact" statistical procedures that do not rely on large sample assumptions will be applied where computationally feasible.

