1. INTRODUCTION

This SAP describes the statistical methods to be used during the analysis and reporting for study EIDD-2801-2003.

Study measurements and assessments, planned statistical methods, and derived variables are summarized in this plan. Planned tables, figures, and listings are specified. All decisions regarding final analyses, as defined in this SAP document, have been made prior to locking the database.

This SAP should be read in conjunction with the study protocol and electronic Case Report Form (eCRF). Any further changes to the protocol or eCRF may necessitate updates to the SAP. This SAP supersedes the statistical considerations identified in the protocol; where considerations are substantially different, they will be so identified. If additional analyses are required to supplement the planned analyses described in the SAP, they may be performed and will be identified in the Clinical Study Report (CSR).

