3.2. Sample Size Considerations

3.2.1. Sample Size Determination

This study is designed to evaluate the antiviral activity of EIDD-2801 by estimating the time (days) until elimination of viral RNA in NP swabs in people who receive EIDD-2801 compared to those who receive a blinded placebo. Kaplan-Meier (KM) estimation will be used with a corresponding exact log-rank test (for Part 1). The median time (days) until first non-detectable SARS-Cov-2 NP swabs will be estimated in each trial arm. Anticipating up to 10% missing data, enrolling n=44 participants total (approximately 22 per arm) in Part 1 will provide 88% power to detect a risk difference (active – placebo) of -35% for the primary endpoint using an alpha=0.10 type I error rate and with viral RNA measured at Days 1, 3, 5, 7, 14, and 28.

For Parts 2 to 9, no formal statistical hypotheses will be tested. In consideration of analysis of secondary virology endpoints in these dose range finding cohorts, separate power calculations were done for Parts 2 to 9. For Parts 2 to 9, sample size sensitivity was estimated based on the combined study parts to compare the change from baseline in viral RNA between participants treated with EIDD-2801 versus participants treated with placebo. A total 96 participants in the

active group and 32 participants in the placebo group will achieve 83% power to detect a between group difference of at least 0.6 SD in SARS-CoV-2 viral RNA change from baseline with a type I error rate of alpha=0.05 using a two-sided test.

The proposed total sample size for the study is up to approximately 172 fully evaluable participants. If participants in a dose group drop out or otherwise have missing or unevaluable primary or key secondary virology endpoint data, additional participants may be enrolled to ensure adequate data at each dose level. The total number of participants to be enrolled will not exceed 204.

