11. CHANGE FROM ANALYSIS PLANNED IN PROTOCOL

Due to lack of availability of subjects in the "early" time from symptom onset stratum, the between group comparison for the time to non-detectable SARS-CoV-2 viral RNA will be performed using an un-stratified log-rank test.

Statistical comparisons of safety endpoints between treatment groups in Part 1 will not be performed. All safety data will be presented descriptively.

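### Part 1 power is stated as 0.88 at a -30% risk difference, but the planned two-sided test on the planned swab days gives about 0.79; the SAP ties the same 88% to -35%

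*Protocol*

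**What the plan says.** Protocol section 10.5 sizes Part 1 for time to undetectable viral RNA, compared by an exact log-rank test at a type I error of 0.10. It claims more than 85% power for a difference "of at least 30% if the evaluable sample size is 19 individuals per arm". It then says that enrolling 44 (about 22 per arm, up to 10% missing) gives 88% power, and lists power by effect: "The power to detect a risk difference (RD) (Drug Placebo) of -30% is 0.88", 0.98 at -40% and above 0.99 at -50%. The values came from 5000 simulated datasets in R.

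On the swab schedule behind the simulation, the same section says: "This assumes collection of NP swabs from all enrolled individuals on Study Days 1, 3, 5, 7, 14, and 28". The table under Figure 8 nevertheless marks a swab on every column, including Days 2, 4 and 10, which are not visit days in the schedule of events.

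Protocol section 10.7.3 fixes the error rate and direction of the test: "a type I error probability of 10% (α =0.10) will be used throughout", and "Throughout, all statistical tests will be two-sided".

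SAP section 3.2.1 keeps n=44, 10% missing data, alpha 0.10 and the six swab days, and says this "will provide 88% power to detect a risk difference (active – placebo) of -35% for the primary endpoint". SAP section 1 says the SAP supersedes the protocol's statistical considerations and that "where considerations are substantially different, they will be so identified". SAP section 11 lists two changes: the primary comparison "will be performed using an un-stratified log-rank test", and the between-group safety comparisons in Part 1 are dropped. The effect size is not mentioned.

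**The concern.** Two things do not fit together. First, the same 88% power, under the same sample size, missing-data allowance, alpha and swab days, is tied to -30% in one document and to -35% in the other. Both cannot be right. Second, the protocol's figure appears not to follow from the test and schedule that the protocol itself lays down.

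Protocol section 10.7.3 calls Part 1 an a priori powered study, and Part 1 is the only part with a formal hypothesis test (SAP section 2.3). A null result read against protocol section 10.5 would suggest a 12% chance of having missed a 30-point difference. If true power is 0.78 to 0.80, that chance is 20 to 22%.

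**Working it through.** **Inputs**

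- 19 evaluable per arm, 1:1 allocation (protocol 10.5 and 10.4). The missing-data allowance gives 22 × 0.9 = 19.8, so 20 and 22 per arm are also shown.
- Two-sided alpha 0.10 (protocol 10.7.3).
- Swabs on Days 1, 3, 5, 7, 14 and 28 (protocol 10.5 and the schedule of events).
- Probability that RNA is still detectable, from the Figure 8 table. The -35% row is not in the table. It is assumed to be placebo minus 35 points, floored at zero, which on these days is also the midpoint of the -30% and -40% rows.

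| Still detectable on Day | 1 | 3 | 5 | 7 | 14 | 28 |
|---|---|---|---|---|---|---|
| Placebo | 100% | 88% | 71% | 52% | 10% | 0% |
| Drug, -30% | 100% | 58% | 41% | 22% | 0% | 0% |
| Drug, -35% (assumed) | 100% | 53% | 36% | 17% | 0% | 0% |
| Drug, -40% | 100% | 48% | 31% | 12% | 0% | 0% |

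**Model**

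The table is labelled as a cumulative probability, so each participant clears once. The chance that the event falls at a visit is the drop since the previous visit. For placebo the drops at Days 3, 5, 7, 14 and 28 are 12, 17, 19, 42 and 10%. For drug at -30% they are 42, 17, 19, 22 and 0%. There is no censoring; missing data enter only through the smaller n.

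At each visit, with d events in total among R at risk (R_drug of them on drug), the unstratified log-rank statistic adds (drug events − d·R_drug/R) to its numerator. It adds d·(R_drug/R)(1 − R_drug/R)(R − d)/(R − 1) to its variance, which corrects for ties. Two-sided rejection is |Z| > 1.645; one-sided is Z > 1.282. The asymptotic test used 100,000 datasets per setting. The permutation (exact) test was run twice, with 4,000 and 5,000 datasets and a standard error of 0.006 to 0.007. Simulated type I error is 0.10.

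**Reproducing the protocol's figures (19 per arm)**

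| Set-up | -30% | -40% |
|---|---|---|
| Protocol 10.5 states | 0.88 | 0.98 |
| Six days, one-sided 0.10 | 0.89 (exact 0.88) | 0.98 |
| All nine tabled days, two-sided 0.10 | 0.89 | 0.98 |
| Six days plus Day 10, two-sided 0.10 | 0.89 | 0.98 |
| Six days plus Days 2 and 4, two-sided 0.10 | 0.81 | 0.96 |

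The stated values come back with a one-sided test, or with a swab on Day 10. Day 10 does the work because the placebo curve falls from 52% to 10% between Days 7 and 14, and the six-day schedule sees that fall only at Day 14.

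**The planned test and schedule (six days, two-sided 0.10)**

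| Evaluable per arm | -30% | -35% | -40% |
|---|---|---|---|
| 19, exact | 0.78 | 0.89 | 0.95 to 0.96 |
| 19, asymptotic | 0.80 | 0.89 | 0.95 to 0.96 |
| 20, exact to asymptotic | 0.80 to 0.81 | 0.90 to 0.91 | 0.96 |
| 22, nothing missing | 0.84 to 0.85 | 0.93 | 0.97 |

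At -50% power is above 0.99, as stated. At -30%, about 25 evaluable per arm are needed to reach 0.88 (0.885 at 25).

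**Could it be simulation noise?** With 5000 datasets the standard error near 0.88 is √(0.88 × 0.12 / 5000) ≈ 0.005. The gap is 0.88 − 0.80 = 0.08 to 0.88 − 0.78 = 0.10, far beyond that.

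**The case against.** The strongest reply is that the governing document is already right. The SAP supersedes the protocol on statistics, and its 88% at -35% reproduces. That is correct and limits the damage: the primary analysis is unaffected. It leaves the protocol's power statement wrong and the change of effect size unexplained.

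A second reply is that the protocol does not give its simulation algorithm, so 0.79 depends on assuming that each participant clears once. This should be stated as an assumption. The main alternative draws detection independently at each visit. It gives about 0.91 to 0.92 at -30% counting the first negative and about 0.93 requiring two consecutive negatives, so it does not yield 0.88 either. It also gives 0.96 to 0.97 at -35%, which would contradict the SAP, and it conflicts with the table's cumulative label.

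Third, 19 per arm is the least favourable reading of 22 with up to 10% missing. Across 19 to 22 evaluable, the chance of missing a 30-point difference is about 15 to 22%. But 19 is the protocol's own number for the claim of more than 85%, and even 22 does not reach 0.88.

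Fourth, SAP section 11 covers changes in analysis, and an effect size in a power statement is arguably not one. That is fair as to where the change belongs. SAP section 1 still promises to identify substantial differences, and no passage identifies this one. Whether 5 points is substantial is a judgement, but on these curves it moves power from about 0.79 to 0.89.

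**Conclusion.** The concern holds. With 19 evaluable per arm, two-sided alpha 0.10 and the six planned swab days, power at -30% is 0.78 to 0.80, not 0.88, and at -40% it is 0.95 to 0.96, not 0.98. The claim of more than 85% for differences of at least 30% fails at its lower end. The SAP's 88% at -35% is sound (0.89), so the two documents give one power for two effects and only the SAP's pairing is supported.

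This rests on the Figure 8 curves, one clearance per participant, no censoring beyond the reduced n, an unstratified test, and the assumed -35% row. The documents do not show whether a one-sided test or the extra swab days produced the protocol's figures. The error concerns what the design was said to deliver and how a null Part 1 result would be read; it does not invalidate the planned test. It should be fixed.

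**What to change.** In protocol section 10.5, restate Part 1 power for 19 evaluable per arm, two-sided alpha 0.10 and swabs on Days 1, 3, 5, 7, 14 and 28: about 79% at -30%, 88 to 89% at -35% and about 95% at -40%. Replace the claim of more than 85% for at least 30% to match. State in the power paragraph that the test is two-sided, and that the simulation treats Figure 8 as a cumulative clearance curve. Mark swabs in the Figure 8 table only on the six scheduled days.

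Use one effect size in both documents. If -35% is kept, add that row to the table and record the change from the protocol in the SAP, most simply in section 11.

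The cost is wording in two documents and a less favourable stated power at -30%. No participants are added, and the test, alpha and sample size do not change.
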